76 To support the evaluation of safety concerns regarding esomeprazole use, a study is proposed to
77 provide further evidence as to whether being prescribed esomeprazole is associated with an increased
78 risk of SD when compared to: (a) being prescribed alternative treatments from the same drug class
79 (i.e., other PPIs); (b) being prescribed alternative treatments from the other drug class (i.e.,
80 histamine type 2 receptor antagonists (H2RAs)); and (c) not being prescribed PPIs or H2RAs despite
81 indications for them (non-initiators). The rationale for using multiple comparator groups is based on
82 the fact that some of the available alternative treatments - which are preferable because of their
83 similar indication (active comparators) - have SD listed as a possible side effect. Ideally, the active
84 comparator should be known to have no effect on the event of interest since it is used to represent the

85 background risk in the disease. (Yoshida et al., 2015) However, impotence is listed as a rare side effect
86 for lansoprazole as well as for H2RAs, and decreased libido is listed as rare side effect for famotidine.
87 (EMC, 2024a, 2024b, 2024c) Therefore, we will opt to also include a non-user comparator (non-
88 initiators), to gain insight into the background risk for sexual dysfunction. Of note, the safety concerns
89 also included omeprazole (i.e. the racemate of esomeprazole and R-omeprazole) considering the partly
90 identical structure shared by esomeprazole and omeprazole. Hence, this study will also examine
91 whether being prescribed omeprazole is associated with an increased risk of SD when compared to the
92 abovementioned comparators.

93 In view of the differences in the definition of SD and risk factors between female and male individuals,
94 and the reported cases which occurred mostly in men and that the majority of primary care recording
95 of SD occurs in males, this study will focus on SD in male individuals only.

96

97 **3. Research question and objectives**

98 Among male patients, is the prescription of:

- 99 1) **Esomeprazole** associated with increased risk of sexual dysfunction (SD) when compared to
100 patients who are:
- 101 a) prescribed other PPIs (namely omeprazole, pantoprazole and lansoprazole)?
102 b) prescribed H2RAs?
103 c) not prescribed either PPIs or H2RAs?
- 104 2) **Omeprazole** associated with increased risk of sexual dysfunction when compared to patients
105 who are:

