	
Inclusion criteria:
 
 • Men aged 18 years or older; • With a recorded diagnosis for any of the following, prior to index date: GERD, gastric and duodenal ulcers, chronic gastroduodenitis, Zollinger-Elison syndrome, OR with a recorded recent history of comedication with any of the following: NSAIDs, acetyl salicylic and derivatives, glucocorticoids, or antithrombotic treatments; • With at least one year of recorded medical history prior index-date. 
Exclusion criteria:
 
 • Those with recorded prescription of any PPIs or H2RAs within one year before index-date; • Those with recorded history of SD OR treatment for SD at any time prior index-date; • Those with recorded history of selected severe central nervous system comorbidities (Section 4.3, Table 1) prior to index-date; • Those with history of Helicobacter pylori (H. pylori) infection or use of fixed PPI-antibiotic treatments for this indication.
Treatment protocols	
Initiate any of the following substances (or none of them in the “non-initiators” cohort) at index-date (see definition below), as monotherapy (i.e., not in combination with another PPI or H2RA).
 
Target arms:
 
 • esomeprazole (target arm [Cohort 1]) • omeprazole (target arm [Cohort 2]) 
Comparator arms:
 
 • pantoprazole (comparator arm [Cohort 3]) in the IQVIA™ Disease Analyser (DA) Germany database) • lansoprazole (comparator arm [Cohort 4]) in the IQVIA™ Medical Research Data (IMRD) UK database) • H2RAs, all combined (comparator arm [Cohort 5]) • non-initiators of either PPIs or H2RAs (comparator arm [Cohort 6])
Assignment procedures	
We will assume treatments are randomly assigned within levels of the covariates identified as potential confounders [see Section 4.6, Potential confounding factors]

Index-date (cohort entry, beginning of follow-up)	
Active treatment arms (including PPIs and H2RAs [Cohort 1 to 5]): The index date will be the date of the initiation of treatment defined as a prescription date for PPIs/H2RAs after a washout window of at least 365 days in which no previous prescription with any PPIs or H2RAs have been recorded.
 
Non-initiator arm [Cohort 6]: Non-initiator comparators will be selected on each date of the recruitment period when esomeprazole/omeprazole initiators start treatment,

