Box 2. Summary of study methods

	matched on birth-year. This date will be the non-initiator comparators index-date . Thus, with regards to treatment, the active treatment arms initiate a treatment on index-date and non-initiator comparators do not.
Outcome	First recorded occurrence of SD, including the following ICD-10 codes: F52.0, F52.1, F52.2, F52.3, F52.6, F52.8, F52.9, N48.4, N94.1, N48.3 [See section 4.6, Outcome]
Follow-up	Patients will be followed-up from index-date up to maximum 1 year. Thus, patients will be followed-up from index-date to the earliest of: date of first occurrence of outcome, loss to follow-up, death (only available in IMRD UK), end of follow-up (1 year) or end of the study period [See Section 4.5, Follow-up period]
Casual contrast of interest	Intention to treat effect, i.e., patients were followed up irrespective of treatment change (main analysis).
Statistical methods	
• Inverse probability of treatment weighting (IPTW) will be used to adjust for confounders measured at cohort entry.• Incidence rates (IR) and cumulative incidence proportions will be estimated for each treatment cohort.• Hazard ratios (HRs) will be estimated using a Cox proportional hazards model.• Cumulative incidence proportions will be estimated for each treatment arm using the Kaplan-Meier estimator.• Sensitivity analyses will include a "Per-protocol" analytical strategy and adjusting for informative censoring at treatment protocol violation. 
[See Section 4.7. Statistical analyses]

115

116

117 4.1. Study design

118 Comparative cohort design, including:

119 a) Active comparator, new user design:

120 • Esomeprazole initiators (target treatment [Cohort 1]) will be compared to the following
121 comparators: pantoprazole [Cohort 3], lansoprazole [Cohort 4], and H2RAs [Cohort 5]
122 initiators.

123 • Omeprazole initiators (target treatment [Cohort 2]) will be compared to the following
124 comparators: pantoprazole [Cohort 3], lansoprazole [Cohort 4], and H2RAs [Cohort 5]
125 initiators.

126 Treatment initiation will be defined as the prescription date for PPIs/H2RAs after a washout
127 window of at least 365 days in which no previous prescription with any PPIs or H2RAs have
128 been recorded. This date will coincide with the cohort entry or start of follow-up in the study,
129 which we will refer to as **index-date**.

130 b) Non-initiator comparator

[figure not shown]

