299 washout) esomeprazole versus patients who: a) initiated other proton pump inhibitors (PPIs, namely
300 omeprazole, pantoprazole/lansoprazole); b) initiated histamine type 2 receptor antagonists (H2RA))
301 and c) patients who did not initiate treatment with either PPIs or H2RA but had received a diagnostic
302 for a PPI or H2RA indication (i.e. non-initiators comparators). Outcome events will be attributed to the
303 baseline treatment protocol regardless of treatment change during follow-up. (i.e., **intention-to-treat
304 analysis (ITT)**).

305

306 4.7.2. Descriptive analysis

307 Descriptive analyses will be performed to describe the study cohorts at baseline in terms of
308 demographic characteristics, lifestyle factors, potential indications, comorbidities, and history of
309 treatment with drugs commonly associated with sexual dysfunction.

310

311 4.7.3. Main statistical analysis

312 **Inverse probability of treatment weighting (IPTW)**

313 Inverse probability of treatment weighting (IPTW) will be used to render the assignment of study
314 treatments independent of the baseline measured covariates, thus minimising the potential
315 confounding effect of these covariates.

316 Using IPTW, the average treatment effect (ATE) in the entire study population will be estimated,
317 assuming that all important confounding variables have been accounted for. For each observation in
318 the study population, the IPTW is the inverse of the probability of receiving the observed treatment

319 conditional on all variables considered sufficient for confounding adjustment. In order to stabilize the
320 weights (i.e., less extreme weights, that are closer to the mean weight of one), the numerator of one
321 will be replaced by the marginal probability of receiving the observed treatment in the study population
322 (i.e., the proportion of observations in the study population with the respective treatment). (Hernan &
323 Robins, 2006) All analyses will then be conducted in the re-weighted population without additional
324 confounding adjustment on the assumption of no unmeasured confounding. To account for weighting
325 the population (essentially multiplying observations by the weight coefficient) robust standard error
326 estimators will be used (Hernan & Robins, 2020).

327 The distributions of baseline covariates before and after weighting was compared between

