328 esomeprazole and the other treatment arms by calculating and plotting standardized mean differences
329 (SMD), with a SMD of <10 used to determine appropriate covariate balance. For each variable, the
330 SMD was the difference in mean (for continuous variables) or proportion (for binary variables) between
331 each treatment arms and the entire study population (which is the target population in the ATE to
332 which the composition of covariates distribution in each treatment arm is standardized), divided by the
333 study population standard deviation of the variable. (McCaffrey et al., 2013)

334

335 **Intention-to-treat (ITT) analysis**

336 The ITT approach chosen for the main analysis will involve following patients from the date of study
337 treatment initiation (i.e., index date) until the earliest of any of the following: first outcome event date,
338 loss to follow-up (e.g., transfer out date from the general practice in IMRD or end of continuous
339 observation of the patient by the practice in IQVIA™ DA Germany, or date of last data collection from
340 the practice), date of death (only available in IMRD) or the end of the study. Consequently, outcome
341 events will be attributed to the baseline treatment regardless of treatment change during follow-up.
342 Moreover, it will be assumed that intercurrent events that may occur during follow-up are independent
343 of the risk of the outcome (i.e., the risk of experiencing the outcome among individuals remaining in
344 the analysis over the course of follow-up is representative of the risk among censored individuals).

345

346 **Incidence rates (IRs)**

347 IRs will be calculated as the number of events occurring during follow-up divided by the total person-
348 time in each treatment-arm. IRs will be presented as number of events per 100 person-years.

349

350 **Cumulative incidence (Incidence proportion)**

351 Survival (i.e., the proportion of the patients included at baseline who have not yet experienced a
352 sexual dysfunction event) over the course of follow-up will be estimated by treatment arm using the
353 Kaplan-Meier method. (Bland & Altman, 1998) The cumulative incidence will be calculated as the
354 complement of survival (i.e., the proportion of the patients included at baseline who have experienced
355 a sexual dysfunction event) at each follow-up time and will be presented as number of events per 100
356 patients.

357

358 **Cox proportional hazards model**

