359 Hazard ratios of sexual dysfunction associated with treatment of interest (esomeprazole) versus
360 comparators will be estimated using a Cox proportional hazards model.

361

362 **4.7.4. Sensitivity analysis**

363 The following sensitivity analyses will be performed to test the validity of the underlying assumptions
364 and the robustness of the study findings:

365 **Applying "per-protocol" (PP) approach:** In this analysis, the follow-up of patients will be censored
366 at the initiation of a PPI or H2RA other than the baseline treatment. Assuming that such censoring is
367 independent of the risk of SD (i.e., non-informative censoring), this analysis will estimate the
368 treatment effect had patients remained on the baseline treatment for the entire follow-up or
369 discontinued the baseline treatment but without initiating an alternative PPI/H2RA.

370 Thus, we will consider a patient to respect the baseline treatment protocol from index-date to the date
371 of crossing over to an alternative treatment arm. Patients will be censored at the earliest of the
372 following events: end of index-treatment, crossing over to an alternative treatment arm, first outcome
373 event date, loss to follow-up (e.g., transfer out date from the general practice in IMRD or end of
374 continuous observation of the patient by the practice in IQVIA™ DA Germany, or date of last data
375 collection from the practice), date of death or at the end of the study period.

376 This approach addresses the situation in which a patient initiates another PPI/H2RA after index-date,
377 which might be problematic if the other PPI/H2RA initiated after index-date and within the 1-year
378 follow-up might cause the outcome event instead of the baseline treatment.

379 It should be noted that the difference between the ITT and PP approach will lie in the follow-up period.
380 The same baseline conditions such as eligibility criteria and washout period before index-date were
381 applied for both analytical approaches.

382 **Adjustment for informative censoring at treatment discontinuation in the PP analysis:** In the
383 per-protocol analysis described above, patients will be censored when they initiate another treatment.
384 Implicit in the per-protocol analysis is an assumption that censoring is independent of the studied
385 outcome, so that this differential treatment selection should not introduce bias.

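### Omeprazole is a target drug in sections 3 and 4.1, but section 4.7 specifies the treatment effect and the Cox hazard ratio for esomeprazole only

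*Protocol*

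**What the plan says.** **Where omeprazole is a target.** Section 3 sets two numbered questions with the same three comparator classes (other PPIs, H2RAs, neither): "Esomeprazole associated with increased risk of sexual dysfunction (SD) when compared to" and "Omeprazole associated with increased risk of sexual dysfunction when compared to patients". Section 2 announces the second aim, saying that the study will also examine "whether being prescribed omeprazole is associated with an increased risk of SD when compared to the" comparators already listed. Box 2 lists "omeprazole (target arm [Cohort 2" beside esomeprazole. Section 4.1 states, under the active-comparator design, "Omeprazole initiators (target treatment [Cohort 2]) will be compared to the following" cohorts, and then sets omeprazole against non-initiators. Table 2 places it under target treatments and gives esomeprazole as its comparator when the roles are reversed.

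**Where only esomeprazole is the target.** Section 4.7.1 describes the estimated effect as the one-year comparison of patients who initiated "washout) esomeprazole versus patients who: a) initiated other proton pump inhibitors (PPIs, namely" omeprazole and pantoprazole/lansoprazole), H2RAs, or neither. The Cox paragraph of 4.7.3 reads "Hazard ratios of sexual dysfunction associated with treatment of interest (esomeprazole) versus" comparators. The lead sentence on covariate balance compares "esomeprazole and the other treatment arms by calculating and plotting standardized mean differences".

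**What section 4.7.3 gives for every arm.** Incidence rates, Kaplan-Meier cumulative incidence and the formal definition of the standardized mean difference (SMD) are written for each treatment arm, and all analyses are to be run in the re-weighted population.

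**The concern.** Section 4.7 does not leave the target drug open for an analysis plan to fill in. It names one drug, and that conflicts with the objectives and the design. Omeprazole's only role in section 4.7 is as a comparator of esomeprazole.

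Two things are at stake. If the analysts follow section 4.7, a stated objective ends with arm-level rates and risks and no prespecified between-arm effect measure for three of its comparisons. If they report omeprazole hazard ratios anyway, a reader cannot tell from the statistical section that these were planned.

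The conflict would also be public. Sections 1 and 4.7.1 are both marked for publication in the HMA-EMA catalogue; the first names both drugs and the second has esomeprazole as the only target.

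**Working it through.** The protocol gives no sample size, power or event number that bears on this point. The check is a comparison of passages and a count.

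**Step 1. Contrasts required.** Section 3 has 2 target drugs × 3 comparator classes = 6 questions (1a-1c, 2a-2c). Each database has five arms: esomeprazole, omeprazole, pantoprazole (Germany) or lansoprazole (UK), H2RAs, and non-initiators.

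**Step 2. Contrasts named in section 4.7.** The answer depends slightly on how the other PPIs are handled:

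| Reading of other PPIs | Distinct contrasts per database | Named in 4.7 | Not named |
|---|---|---|---|
| Drug by drug | 4 (esomeprazole vs each other arm) + 4 (omeprazole vs each other arm) − 1 shared = 7 | 4 | 3 |
| Pooled as one group | 3 + 3 = 6 | 3 | 3 |

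Drug by drug, the three unnamed contrasts are omeprazole versus pantoprazole/lansoprazole, versus H2RAs and versus non-initiators. Pooled, they are 2a, 2b and 2c; here 2a is not a reciprocal of 1a, because the two comparator groups differ. Over two databases the unnamed total is 2 × 3 = 6 under either reading, out of 14 or 12.

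**Step 3. Can the missing hazard ratios be derived?** Omeprazole versus esomeprazole is 1 / HR(eso vs ome) under the drug-by-drug reading. For any other arm X, if one weighted Cox model contains all arms:

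log HR(ome vs X) = log HR(eso vs X) − log HR(eso vs ome)

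Var = Var[log HR(eso vs X)] + Var[log HR(eso vs ome)] − 2 Cov of the two

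In a joint fit the covariance is available, so the estimate and its interval follow. In separate two-arm fits the covariance is not produced, and the identity need not hold exactly. The protocol does not say which kind of model will be used, so derivability is not assured.

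**Step 4. Balance.** The lead sentence compares esomeprazole with the other arms. The next sentence defines the SMD as each arm's difference from the entire study population, divided by that population's standard deviation. Under that definition omeprazole and each of its comparators are assessed. If two arms each lie within d of the population, they lie within 2d of each other on the same scale. The two sentences disagree about the reference group, but omeprazole is not left out of the diagnostic.

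**Step 5. Arm-level results.** Incidence rates and cumulative incidence cover every arm in the weighted population, so omeprazole has adjusted absolute results.

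**The case against.** The strongest reply is that this is leftover drafting. Section 2 presents omeprazole as an addition to a question first posed for esomeprazole, and the parenthesis in the Cox sentence looks like text that was not updated. Nothing in section 4.7 excludes omeprazole. Box 2 lists Cox hazard ratios without naming a drug, section 4.1 and Table 2 state the omeprazole comparisons, and the per-protocol rules refer to the baseline treatment in general. An analyst reading the whole document would be unlikely to drop half of the objectives, and section 7 mentions an analysis plan where a list of contrasts could sit.

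Much of this stands, and it limits the point. A reader might infer that omeprazole gets no estimate at all, or that nothing checks whether the weights worked for its comparisons. The document supports neither reading: weighted rates and risks are planned for every arm, and the SMD definition covers every arm. A reader might also count objective 2a as wholly uncovered; drug by drug, its esomeprazole part is the reciprocal of a named hazard ratio.

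What does not stand is that the general wording elsewhere settles the matter. The section that governs the analysis names a single treatment of interest, and a generic line in a summary box does not override it. An analysis plan that is not shown may list the contrasts, but it cannot remove a contradiction between sections of this protocol.

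**Conclusion.** The point holds as an inconsistency between the objectives and the statistical section. Section 4.7 specifies the comparative estimate for esomeprazole only. Three omeprazole hazard ratios per database, six in all, are called for by section 3 and not specified in 4.7. This takes section 4.7 literally. If one joint weighted Cox model is fitted and PPIs are compared drug by drug, all three can be obtained from the same fit, and the defect is then one of specification and reporting. If separate esomeprazole-versus-comparator models are fitted, no model in section 4.7 estimates them directly.

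Arm-level results and balance diagnostics for omeprazole are planned and are not in question. The correction should be made before the analysis is run, because it settles which hazard ratios for objective 2 count as prespecified.

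**What to change.** - In 4.7.1 and in the Cox paragraph of 4.7.3, replace esomeprazole as the sole treatment of interest with each target treatment (esomeprazole; omeprazole) versus each comparator in section 3, under the same ITT and per-protocol rules.
- State whether these hazard ratios come from one joint weighted model or from separate models, and whether the other PPIs are compared drug by drug or pooled.
- Rewrite the lead balance sentence so that it matches the SMD definition that follows it: every arm against the entire study population.

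The cost is a few sentences and a little more analysis. No new data are needed, since the omeprazole cohort is already part of the design.

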386 In this analysis, we will adjust for potential selection bias via informative censoring, by reweighting
387 patient observations using the inverse of the probability of being censored at the initiation of another
388 treatment conditional on the same confounders selected at baseline (i.e., outcome risk factors
389 potentially associated with treatment initiation) but updating their values during follow-up. (Hernan et
390 al., 2000; Robins et al., 2000)

391

392 Analyses will be done using SAS Enterprise Guide 7.1 software.

393

394 **4.7.5. Sample size**

395 The sample size will be driven by the availability of individuals with exposures and outcomes within
396 each database and no *a priori* sample size requirement will be stipulated.

397

398 **4.8. Quality control**

399 The study will be conducted according to the ENCePP code of conduct (European Medicines Agency
400 2018).

401 Standard operating procedures or internal process guidance will be adhered to for the conduct of the
402 study. These procedures include rules for secure and confidential data storage, quality-control
403 procedures for all aspects of the study from protocol development to the reporting of the results.

404 All documents will undergo at least one round a review by an experienced reviewer, while the results
405 from the statistical analysis will be either reviewed or checked via double coding.

406 The quality control of the data is the responsibility of the data holder.

407 **4.9. Limitations of the research methods**

408 Exposure misclassification may exist since neither OTC drug use nor medication use during
409 hospitalisation are captured in the included databases. This is a particular issue because of the availability
410 of OTC PPIs has increased over time (Johnson et al., 2017) and, probably their OTC use. Additionally,
411 information on the actual duration of treatment corresponding to each prescription is not available and
412 is difficult to estimate since patients may be prescribed large packs and instructed to use the drug as
413 needed, with possible discontinuation/restart and dose-variation over time. Moreover, whether patients
414 collected their prescriptions or consumed the prescribed medication is unknown. Due to this uncertainty
415 and considering information from individual case reports about the latency of effect, we chose to follow
416 patients for a maximum of one year and attribute the entire follow-up to the index treatment unless

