417 another treatment was initiated. It should be noted that, in the analysis comparing with non-initiators,
418 we restricted the study population to patients with chronic indications, for which treatment is likely
419 chronic.

420 To our knowledge, the accuracy of diagnostic coding for sexual dysfunction has not been assessed in the
421 primary care databases available. However, the nature of the diagnosis means that its recording in
422 primary care records could be reasonably accurate, particularly for sexual dysfunction in male individuals.
423 Nonetheless, this assumption should be treated cautiously. In the UK, the patent for Viagra expired in
424 June 2013, which followed a drop by 93% in the price of generic preparations of sildenafil compared to
425 the price of branded Viagra (Connelly, 2017). Besides, Sildenafil has been available OTC without
426 prescription from UK pharmacies since 2017 and, therefore, patients have no longer needed to see their
427 doctor to get a diagnosis ever since. (MHRA, 2017) These events led to marked changes in diagnosis
428 coding practices of erectile dysfunction during 2013-2014 and marked decrease of coding for impotence
429 by GPs since 2017 which are reflected in the distribution of outcome events over calendar time. In
430 IQVIA™ DA Germany the reporting of male sexual dysfunction appears stable after 2005. To account for
431 uncertainties around potential misclassification due to changes in diagnostic criteria or coding practices
432 over time, calendar period will be adjusted for in the analysis.

433 It also needs to be considered that patient's medical history, as captured by GP practices included in
434 the study, may be incomplete, particularly in the IQVIA DA Germany database. In Germany, there is
435 no mandatory GP system and patients have free doctor choice. A specialist can be consulted without
436 referral from the GP. As a result, data are collected from visits to various medical practices which are
437 not linked by a unique patient identifier. Therefore, the entire medical history of patients might be
438 fragmented and for that reason there is a risk of exposure, outcome and covariates misclassification.
439 However, this misclassification will affect both target and comparator groups.

440 Although confounding by indication represents a common source of bias, it is not likely that the main

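### The per-protocol sensitivity analysis carries two incompatible censoring rules: its stated effect keeps men who stop without switching, while its event list censors them

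*Protocol*

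**What the plan says.** The per-protocol text is in Protocol section 4.7.4. Its first paragraph censors follow-up when a patient starts a PPI or H2RA other than the baseline one. The effect it claims to estimate covers patients who stayed on treatment for the whole follow-up and also those who "discontinued the baseline treatment but without initiating an alternative PPI/H2RA". The second paragraph opens by saying that a patient respects the baseline protocol until crossing over. Its next sentence gives the censoring events: "following events: end of index-treatment, crossing over to an alternative treatment arm, first outcome" event, and then loss to follow-up, death and end of study.

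The weighted version that follows is titled "Adjustment for informative censoring at treatment discontinuation in the PP analysis". The text below that title describes only censoring when another treatment is initiated, and the weights are built on the probability of that event alone.

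Section 4.9 says that "information on the actual duration of treatment corresponding to each prescription is not available and" is difficult to estimate, citing large packs, as-needed use and restarts. It gives this uncertainty, together with the latency seen in case reports, as the reason to follow "patients for a maximum of one year and attribute the entire follow-up to the index treatment unless" another treatment was started.

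**The concern.** A man who stops his index drug and starts nothing else is followed for up to a year under the first paragraph and censored on stopping under the list. Whoever programs the analysis must choose, and the choice changes both the follow-up and the effect being estimated. If the choice is left open, it could be made after results are seen.

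If the list is followed, the estimate no longer matches the effect the protocol declares. The weighted analysis, whose purpose is to deal with informative censoring, would also leave one of its censoring events unadjusted. Stopping could plausibly be related to the outcome: the Background reports improvement after discontinuation in 15 case-report patients. In the comparison with non-initiators, only the treated arm has an index treatment that can end, so follow-up would be shortened on one side only.

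**Working it through.** The protocol states no figure on this point, so there is none to reproduce. The check is mainly a comparison of texts, followed by a simple calculation of scale.

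**Step 1. Which statements support which rule**

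| Place in the Protocol | Censor at a switch only | Censor at end of treatment |
|---|---|---|
| 4.7.4, opening definition | yes | |
| 4.7.4, stated effect (discontinuers kept) | yes | |
| 4.7.4, sentence on respecting the baseline protocol | yes | |
| 4.7.4, list of censoring events | | yes, in addition to crossover |
| 4.7.4, title of the weighted analysis | | yes (discontinuation) |
| 4.7.4, text and weights under that title | yes | |
| 4.9, attribution of follow-up | yes | |

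The list entry cannot be read as another name for switching, because crossing over is the next, separate item.

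**Step 2. Whether the list rule can be carried out as written**

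- *Date.* Section 4.9 says actual duration per prescription is not available and hard to estimate. The Protocol gives no rule for deriving an end date.
- *Non-initiators (Cohort 6).* They have no index treatment. In a rule that takes the earliest of several events, this event never occurs for them. The rule still operates, but asymmetrically.
- *Weights.* They model initiation of another treatment only. End-of-treatment censoring would be unweighted.

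**Step 3. Scale, under a stated assumption**

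Inputs from section 4.5: recommended duration of 4-8 weeks for PPIs and 8-12 weeks for H2RAs; maximum follow-up of one year (52 weeks). Assumption: index treatment ends exactly at the recommended duration, in a patient who would otherwise be followed for the full year.

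Share of the window removed = 1 − duration / 52.

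- PPI, 4 weeks: 1 − 4/52 = 0.923
- PPI, 8 weeks: 1 − 8/52 = 0.846
- H2RA, 8 weeks: 1 − 8/52 = 0.846
- H2RA, 12 weeks: 1 − 12/52 = 0.769

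So the list rule removes about 85-92% of the window for PPI initiators and 77-85% for H2RA initiators. Under the switch-only rule a patient who never switches loses nothing.

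Under the same assumption, PPI follow-up would end at 28-56 days. The Background gives symptom onset in the reported male cases as a few days to five months (5 × 365/12 ≈ 152 days), so the later part of that range would fall after censoring.

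**Step 4. The switching event itself**

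The definition refers to any PPI or H2RA other than the baseline one; the list refers to an alternative treatment arm. Section 4.6 limits the study PPIs to three per database, but Annex 2 also lists lansoprazole for Germany, and pantoprazole and rabeprazole for the UK. A switch to one of these might count under one wording and not under the other. This is a secondary ambiguity that the same edit can settle.

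**The case against.** The best defence is that the list entry is a slip. The switch-only rule is stated repeatedly in section 4.7.4 and again in section 4.9, and the weights already match it. Against it stand one list entry and one word in a title. That is a fair account of the likely intention, and it shows which way the text should be reconciled. It does not remove the contradiction: the event list is the operational sentence, and the title of the weighted analysis points the same way as the stray entry.

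A second defence is that an analysis plan not shown here could define an end-of-treatment date from prescriptions. It could, and the lack of an algorithm in the Protocol is not itself a fault. But a date would not reconcile the list with an effect that keeps discontinuers, nor bring the event into the weights.

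Several stronger readings are tempting and are not supported:

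- *That the main result is compromised.* The main analysis is intention to treat, and its rates, cumulative incidences and hazard ratios do not use this rule.
- *That 85-92% of follow-up would actually be lost in every treated arm.* That treats a recommended duration as the real one and overlooks the longer H2RA range. The Protocol selects indications for which it expects treatment to be chronic.
- *That events would be lost from treated arms only.* This one-sidedness arises only against non-initiators. In the active-comparator contrasts both arms have an index treatment, and censoring removes person-time as well as events.
- *That an end date cannot be determined at all.* Section 4.9 does not go that far.
- *That men are shown to stop before the outcome is coded.* The case reports make this plausible and no more.

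**Conclusion.** The point holds for the per-protocol sensitivity analysis and its weighted version, which are the two sensitivity analyses set out in section 4.7.4. The event list contradicts the stated effect, and the title of the weighted analysis contradicts the text beneath it. Followed literally, the list gives an estimate that does not match its declared target and carries censoring that the weights do not address. This is an error in what is written, not a detail left for later.

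The contradiction itself rests on the text alone. The percentages rest on the assumption that treatment ends at the recommended duration. They show that the two rules could differ greatly, and they do not predict the actual loss.

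**What to change.** In section 4.7.4:

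1. Delete the *end of index-treatment* entry from the list of censoring events.
2. Change the title of the weighted analysis so that it refers to informative censoring *at initiation of another treatment*.
3. Use one censoring event in the definition, the list and the weight model: *first prescription of any PPI or H2RA other than the baseline treatment (for non-initiators, of any PPI or H2RA), whether or not it is a study arm*.

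If the sponsor wishes to keep end of treatment as a censoring event, the Protocol must instead define its date, include the event in the censoring weights, restate the effect being estimated so that it no longer covers discontinuers, and say how non-initiators are handled.

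The first route costs a few words of protocol text and one programming definition. It needs no new data and leaves the main analysis as it is. The second route needs a derived end date and an additional censoring model.
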